8.6. ASSESSMENT OF DOSE PROPORTIONALITY FOR SEL-037

Single and multiple dose PK parameters for SEL-037 PK concentrations or uricase activity C_{max} , C_{min} , AUC_{0-last} , AUC_{tau} normalized by dose of SEL-037 will be compared between cohorts 1, 3, 5, 7, 11 with 0.2 mg/kg and 2, 4, 6, 8, 10, 12 with 0.4 mg/kg doses of SEL-037 using ANOVA model separately for Parts A and B and each treatment period and combined data for Parts A and C (treatment periods 1-3 only).

For Part A of each cohort, the dose of SEL-110 will be included as fixed effect in this comparison.

The dose normalized PK parameters for SEL-037 will be presented on box plots for each treatment and part separately and overall for all cohorts with the same dose level for comparison for Parts A and B and separately for combined data Parts A and C (treatment periods 1-3).

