4. INTRODUCTION

4.1. Investigational product

SEL-212 is a combination product containing SEL-037 (pegsiticase, Recombinant Pegylated Candida Urate Oxidase) and SEL-110 a drug product consisting of a biodegradable polymeric nanoparticle consisting of PLA (poly(D,L-lactide)) and PLA-PEG (poly(D,L-lactide)-block-poly-(thylene-glycol)) encapsulating rapamycin.

SEL-037 (pegsiticase; Recombinant Pegylated Candida Urate Oxidase) is a lyophilized recombinant uricase (urate oxidase) conjugated to multiple 20 kDa molecular weight polyethylene glycol (PEG) molecules. The uricase component of SEL-037 is cloned from the yeast *Candida utilis* (Koyama, 1996) and expressed in *Escherichia coli* for production (Bomalaski, 2002). The uricase component catalyzes the conversion of uric acid to the more soluble compound allantoin that is then readily excreted and is being developed to reduce hyperuricemia in chronic gout patients refractory to conventional therapy. SEL-037 has been given to humans in a single ascending dose escalation Phase 1 clinical study SEL-037/101 and was given in a single fixed dose of 0.4 mg/kg with or without SEL-110 in a Phase 1b clinical study SEL-212/101.

SEL-110, (PLA, PLA-PEG nanoparticle encapsulating rapamycin) is designed to inhibit the formation of anti-drug antibodies (ADAs) when concomitantly administered with a biologic drug during the first few doses of the biologic. When SEL-110 is dosed in this manner it induces durable, antigen-specific immune tolerance to the biologic therapeutic in animal models. SEL-110 has demonstrated the ability to induce antigen specific immune tolerance to pegylated uricase (SEL-037) in wild type mice, uricase deficient (knock-out) mice, rats and cynomolgus monkeys. SEL-110 was tested in man for the first time in a single ascending dose clinical study SEL-212/101. All of the proposed SEL-110 alone doses (0.03 mg/kg, 0.1mg/kg, 0.3mg/kg and 0.5mg/kg) have been completed. We believe we have identified a MTD in this clinical study for SEL-110 of 0.3 mg/kg as discussed further in Section 4.3.2.2.

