6.2. Number of Subjects

Number of patients (planned): In Part A and Part B, approximately 100 subjects will be divided into 11 dosing cohorts, each consisting of 6-20 subjects. Cohorts 1-10 are closed to enrollment but are permitted to be re-opened to increase the enrollment to the maximum total number of subjects permitted. Cohorts 11 and 12 will continue enrolling up to 20 subjects per cohort. Cohort 1 will receive SEL-037 (pegsiticase alone, 0.2 mg/kg), Cohort 2 will receive SEL-037 (pegsiticase alone, 0.4 mg/kg), Cohort 3 will receive SEL-212 (with 0.05 mg/kg of SEL-110 + 0.2 mg/kg pegsiticase), Cohort 4 will receive SEL-212 (with 0.05 mg/kg of SEL-110 + 0.4 mg/kg pegsiticase), Cohort 5 will receive SEL-212 (with 0.08 mg/kg of SEL-110 + 0.2 mg/kg pegsiticase), Cohort 6 will receive SEL-212 (with 0.08 mg/kg of SEL-110 + 0.4 mg/kg pegsiticase), Cohort 7 will receive SEL-212 (with 0.1 mg/kg of SEL-110 + 0.2 mg/kg pegsiticase), Cohort 8 will receive SEL-212 (with 0.1 mg/kg of SEL-110 + 0.4 mg/kg pegsiticase), Cohort 10 will receive SEL-212 (with 0.125 mg/kg of SEL-110 + 0.4 mg/kg pegsiticase), Cohort 11 will receive SEL-212 (with 0.15 mg/kg of SEL-110 + 0.2 mg/kg pegsiticase), and Cohort 12 will receive SEL-212 (with 0.15 mg/kg of SEL-110 + 0.4 mg/kg pegsiticase). Note that Cohort 9 is intentionally omitted from this protocol in order to maintain the cohort numbering convention of associating even numbered cohorts with the 0.4 mg/kg SEL-037 dose.

In Part C, up to 40 patients naïve to SEL-212 will be enrolled. Patients enrolled in Cohort 13 will receive SEL-212 (0.15 mg/kg SEL-110 + 0.2 mg/kg SEL-037). Patients enrolled in Cohort 15 will receive an initial induction dose of SEL-212 (0.15 mg/kg SEL-110 + 0.2 mg/kg SEL-037) and, then, four subsequent doses of SEL-212 (0.10 mg/kg SEL-110 + 0.2 mg/kg SEL-037). Patients enrolled in Cohort 17 will receive SEL-212 (0.10 mg/kg SEL-110 + 0.2 mg/kg SEL-037). (Note: Cohorts 14 and 16 are intentionally omitted from this protocol in order to maintain the cohort numbering convention of associating odd numbered cohorts with the 0.2 mg/kg SEL-037 dose.)

Subjects who withdraw early or have significant protocol deviations or compliance issues may be replaced at the discretion of the Sponsor to assure completion of the objectives of the clinical study and to maintain the integrity of the data set.

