6.3.1. Stopping Rules in an Individual Subject or in a Cohort

For this clinical trial a treatment period is defined as period of time from the beginning of dosing of the first study drug on a given dosing day (ie, Either saline placebo or SEL-110 during Part A of the study and SEL-037 during Part B of the study) to the beginning of the next scheduled dose of study drug, and has a typical duration of 28 days.

For Part C (Cohorts 13, 15, and 17), a treatment period is defined as the period of time from the beginning of dosing of SEL-212 to the beginning of the next scheduled dose of study drug.

Individual

For subjects in Cohorts 1 and 2, any subject who has a weekly serum uric acid value ≥ 6 mg/dl or $>50\%$ of their baseline (where baseline value refers to the pre-dose serum uric acid level from visit 4, Day 0, treatment period 1) at Day 21 of their current treatment cycle will not be eligible for the next dosing of SEL-037. The subject will be followed for 30 days post the last dose of study drug at which time they will have an End of Study assessment and their participation in the study will be terminated.

In Cohorts 3-8, 10-13, 15, and 17 only subjects whose ambient blood samples indicate a serum uric acid (sUA) value less than or equal to 1.0 mg/dL at any of the Day 21 visits will be eligible for the next dosing of SEL-212 (or SEL-037). All other subjects will be followed for 30 ± 2 days post the last dose of study drug at which time all of the End of Study assessments will be completed and their participation in the study will be terminated.

Cohort

If 5 subjects in any of Cohorts 1-5 or 7, or if 10 subjects in any of Cohorts 6, 8, 10, 11, or 12 have met the requirements for individual stopping of their participation in the trial as described above or have been stopped based on Section 6.4 then that cohort will no longer have any additional subjects enrolled in it. Those subjects who have been enrolled will continue until they fulfill the requirements

Study: SEL-212/201 Version: 7.1	Effective Date March 19, 2018
------------------------------------	----------------------------------

for individual stopping or complete the clinical trial treatment periods. If they continue to meet the requirements for continued participation they may continue in Part B of the study.

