In Part A and Part B, approximately 100 subjects will be divided into 11 dosing cohorts, each consisting of 6-20 subjects. Cohort 1 will receive SEL-037 (pegsitacase alone, 0.2 mg/kg). Cohort 2 will receive SEL-037 (pegsitacase alone, 0.4 mg/kg), Cohort 3 will receive SEL-212 (with 0.05 mg/kg of SEL-110 + 0.2 mg/kg pegsitacase), Cohort 4 will receive SEL-212 (with 0.05 mg/kg of SEL-110 + 0.4 mg/kg pegsitacase), Cohort 5 will receive SEL-212 (with 0.08 mg/kg of SEL-110 + 0.2 mg/kg pegsitacase), Cohort 6 will receive SEL-212 (with 0.08 mg/kg of SEL-110 + 0.4 mg/kg pegsitacase), Cohort 7 will receive SEL-212 (with 0.1 mg/kg of SEL-110 + 0.2 mg/kg pegsitacase) and Cohort 8 will receive SEL-212 (with 0.1 mg/kg of SEL-110 + 0.4 mg/kg pegsitacase), Cohort 10 will receive SEL-212 (with 0.125 mg/kg of SEL-110 + 0.4 mg/kg pegsitacase), Cohort 11 will receive SEL-212 (with 0.15 mg/kg of SEL-110 + 0.2 mg/kg pegsitacase), and Cohort 12 will receive SEL-212 (with 0.15 mg/kg of SEL-110 + 0.4 mg/kg pegsitacase). Note that Cohort 9 is intentionally omitted in order to maintain the cohort numbering convention of associating even numbered cohorts with the 0.4 mg/kg SEL-037 dose.

In Part C, up to 40 patients naïve to SEL-212 will be enrolled. Patients enrolled in Cohort 13 will receive SEL-212 (0.15 mg/kg SEL-110 + 0.2 mg/kg SEL-037). Patients enrolled in Cohort 15 will receive an initial induction dose of SEL-212 (0.15 mg/kg SEL-110 + 0.2 mg/kg SEL-037) and, then, four subsequent doses of SEL-212 (0.10 mg/kg SEL-110 + 0.2 mg/kg SEL-037). Patients enrolled in Cohort 17 will receive SEL-212 (0.10 mg/kg SEL-110 + 0.2 mg/kg SEL-037). (Note: Cohort 14 and 16 are intentionally omitted in order to maintain the cohort numbering convention of associating odd numbered cohorts with the 0.2 mg/kg SEL-037 dose.) Subjects who withdraw early, or have significant protocol violations or compliance issues may be replaced at the discretion of the Sponsor to assure completion of the objectives of the clinical study and to maintain the integrity of the data set.

Statistical Analysis Plan

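### SAP 8.6 names no SEL-110 term for the Part B comparison of 0.2 and 0.4 mg/kg SEL-037; the likely cost is lost precision, with only a small bias unless Part B numbers are clearly uneven across cohorts

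*SAP*

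**What the plan says.** SAP 8.6 takes SEL-037 Cmax, Cmin, AUC0-last and AUCtau, normalised by SEL-037 dose, and compares "cohorts 1, 3, 5, 7, 11 with 0.2 mg/kg and 2, 4, 6, 8, 10, 12 with 0.4 mg/kg doses of SEL-037". The method is an analysis of variance, fitted once per Part and once per period. The only statement about SEL-110 in that comparison is "For Part A of each cohort, the dose of SEL-110 will be included as fixed effect in this comparison". The section does not say whether the term is linear or categorical, and it sets no test level or acceptance interval.

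Nothing nearby fills the gap for Part B:

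- SAP 8.7 models SEL-110 dose separately within each SEL-037 level, so it yields no adjusted 0.2 versus 0.4 contrast. Its Part B versus Part C contrasts involve only 0.2 mg/kg cohorts.
- The box plots in SAP 8.6, the summaries in SAP 8.3 and 8.4, and the antibody comparisons in SAP 10.4 and 10.5 are descriptive.

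**The concern.** SEL-110 is not given in Part B, which may be why the term stops at Part A. The protocol nevertheless gives reasons to expect its effect to carry over:

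- Protocol 4.1 says of SEL-110: "When SEL-110 is dosed in this manner it induces durable, antigen-specific immune tolerance to the biologic therapeutic in animal models".
- Protocol 4.3.2.3 reports that SEL-110 appeared to suppress anti-uricase antibodies in a dose-related way.
- Protocol 4.3.2.1 links anti-drug antibodies to faster SEL-037 clearance.
- Protocol 4.5.1 suggests that the first treatment period may decide later antibody status.

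Part A SEL-110 dose is therefore a plausible source of variation in Part B SEL-037 exposure. If it is left out, that variation goes into the residual and widens the interval for the 0.2 versus 0.4 contrast. If the two groups also differ in average prior SEL-110, part of the difference can pass for non-proportionality of SEL-037, or mask it.

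**Working it through.** SAP 8.6 gives no figure to reproduce, so this check works from the design.

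**Inputs from the documents.** Prior SEL-110 doses are 0, 0.05, 0.08, 0.1 and 0.15 mg/kg in the 0.2 group, and the same plus 0.125 mg/kg (Cohort 10) in the 0.4 group. On size, SAP 3.7 says "approximately 100 subjects will be divided into 11 dosing cohorts, each consisting of 6-20 subjects".

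**Assumptions, none from the documents.** Analysis on the log scale; a log-linear carry-over in which R is the exposure ratio for prior SEL-110 of 0.15 versus 0 mg/kg, with R = 1, 1.5, 2 or 3; within-cohort CV of 50% (30% and 70% as a range); 9 subjects per cohort, so 45 versus 54.

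**Balance with equal cohorts.** Mean prior dose is 0.380/5 = 0.0760 in the 0.2 group and 0.505/6 = 0.0842 in the 0.4 group. The difference is d = 0.0082 mg/kg, all of it from Cohort 10.

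**Bias.** The spurious 0.4/0.2 ratio is R^(d/0.15). At R = 2 this is 2^(0.0082/0.15) = 1.038.

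**Precision.** Let σ² = ln(1 + 0.5²) = 0.223 and b = ln(R)/0.15. The within-group sum of squares of prior dose is S = 9 × (0.01252 + 0.01452) = 0.243.

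- SE reported by the unadjusted model: √[(σ² + b²S/97)(1/45 + 1/54)]
- SE with a linear term: √[σ²(1/45 + 1/54 + d²/S)]

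| R | Spurious ratio | SE unadjusted | SE linear term | Unadjusted / linear |
|---|---|---|---|---|
| 1 | 1.000 | 0.095 | 0.096 | 0.997 |
| 1.5 | 1.022 | 0.099 | 0.096 | 1.037 |
| 2 | 1.038 | 0.106 | 0.096 | 1.110 |
| 3 | 1.062 | 0.121 | 0.096 | 1.262 |

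A categorical term gives an SE of √[σ²(2/45)] = 0.100 at every R, because Cohort 10 then has no partner and drops out of the contrast. For R from 1.5 to 3, the last column runs from 1.10 to 1.60 at a CV of 30% and from 1.02 to 1.15 at 70%. Nine per cohort is optimistic for Part B. With fewer but equal numbers both SEs grow together and their ratio hardly changes.

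**Unequal cohorts.** Protocol 6.3.1 closes cohorts at different counts: "If 5 subjects in any of Cohorts 1-5 or 7, or if 10 subjects in any of Cohorts 6, 8, 10, 11, or 12". Pairs 5/6 and 7/8 therefore have different limits.

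- Suppose 6 subjects in each of Cohorts 1 to 5 and 7, 10 in each of 6, 8 and 10, and 20 in each of 11 and 12. The means are 4.38/44 = 0.0995 and 6.35/62 = 0.1024, so d = 0.0029 and the ratio at R = 2 is 1.013.
- At the extremes, with every cohort set at 6 or 20 to push the means apart, d runs from 0.0583 − 0.0997 = −0.041 to 0.1075 − 0.0514 = +0.056. The ratio at R = 2 is then 0.83 to 1.30.
- To reach a ratio of 1.10 at R = 2, d must be 0.15 × ln(1.10)/ln(2) = 0.021 mg/kg, about 2.5 times the design difference.

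**The case against.** The strongest reply is that the design already does most of the work. Every SEL-110 dose except 0.125 mg/kg appears with both SEL-037 doses, so near-equal numbers leave little to confound. That stands.

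A reader might go further than the documents allow and infer that the Part B comparison is confounded and its type I error inflated. Such results can be produced: mean prior doses of 0.081 versus 0.119, or 0.135 versus 0.101 mg/kg, give ratios of roughly 1.11 to 1.3, or 0.78 to 0.91. Those mixes are in no document, and SAP 8.6 sets no test level to inflate. With equal cohorts the error goes the other way. The reported SE is too wide, so a nominal 5% test of a truly proportional drug would reject about 3 to 4% of the time at a CV of 50% and R of 1.5 to 3.

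Selection also cuts against a large effect. In the SEL-110 cohorts of Parts A and B, only subjects with serum uric acid at a "value less than or equal to 1.0 mg/dL at any of the Day 21 visits will be eligible for the next dosing" go on (Protocol 6.3.1). That tends to remove subjects who have lost SEL-037 activity, which is the route by which SEL-110 history would act, so the effect among survivors is probably weaker than in all subjects. Adding the SEL-110 term does not undo this selection, and Cohorts 1 and 2 pass under a different uric acid rule.

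The evidence for carry-over is limited too: the durability statement concerns animal models, and the human dose-response comes from a single-dose study. These points reduce the expected size. They do not explain why a term judged relevant in Part A is omitted in Part B.

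**Conclusion.** The omission is real and nothing else in the SAP adjusts the Part B contrast. If prior SEL-110 matters at all, the main expected cost is precision: an unadjusted SE about 4 to 26% larger for an assumed 1.5 to 3-fold effect, at a CV of 50% and 9 per cohort. The accompanying bias is small, a ratio of about 1.02 to 1.06 with equal cohorts. Material bias requires Part B numbers that are clearly unequal across cohorts; the closure and Day 21 rules make that possible, but the documents do not show it. If prior SEL-110 has no effect, nothing is lost by the present plan. The comparison serves a secondary PK objective, and the primary safety objective is untouched.

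**What to change.** In SAP 8.6, state that the Period 4 and Period 5 models for the 0.2 versus 0.4 mg/kg contrast include the subject's Part A SEL-110 dose, with 0 for Cohorts 1 and 2, as a linear covariate. The form should be fixed in advance: a categorical term would use up to five degrees of freedom and take Cohort 10 out of the contrast.

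SAP 8.7 borrows the 8.6 model for its Part B versus Part C contrasts, so the text should say that the new term is left out there, where SEL-110 is the effect of interest.

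The cost is one model term and one degree of freedom, on data already held. The downside is small. The term relies on a linear form, and it gains nothing if prior SEL-110 has no effect (SE 0.096 against 0.095). The report should state as a limit that the adjustment does not correct the Day 21 uric acid selection into Part B.

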8.7. ASSESSMENT OF EFFECT OF VARIOUS DOSES OF SEL-110 ON PHARMACOKINETICS OF SEL-037

Effect of co-administration of various doses of SEL-110 on pharmacokinetics of SEL-037 PK parameters for serum concentrations or uricase activity for cohorts 1, 3, 5, 7, 11 (SEL-037 dose 0.2 mg/kg) and 2, 4, 6, 8, 10, 12 (SEL-037 dose 0.4 mg/kg) separately (SEL-110 dose in cohorts 1 and 2 will be set to 0) will be performed by a linear mixed-effect model:

$$PKparam(SEL - 037) = \alpha + s_i + \beta \times Dose(SEL - 110) + e_i$$

α : population mean intercept

β : population mean slope

s_i : random effect of subject i on the intercept, iid $N(0, \sigma_s^2)$

e_i : residual, iid $N(0, \sigma_e)$ for subject i

Statistical Analysis Plan

the PK parameters and dose of SEL-110 will not be log-transformed to allow inclusion of 0 dose of SEL-110 into the model

P value will be calculated for slope and intercept. If the p-value of the slope is less than 0.05, a direct relationship is declared. If p value for slope will be >0.05 the result will be interpreted as lack of effect of SEL-110 on pharmacokinetics of SEL-037.

SEL-110 co-administration effect will also be explored graphically with scatter plots of C_{max} , AUC_{0-last} and AUC_{0-inf} for SEL-037 serum concentrations or uricase activity vs dose levels of co-administered SEL-110 including 0 dose for placebo.

The example SAS code will be:

```
PROC MIXED DATA=data_set_name;  
CLASS treatment;  
MODEL PK Parameter = dose /DDFM=KR;  
LSMEANS dose / CL;  
RUN;
```

Additionally the effect of SEL-110 on PK of SEL-037 will be performed by comparison of data from Parts B vs Part C for treatment periods 4-5 using ANOVA model as described in the Section 8.6 of the SAP.

The contrasts will include:

- Cohort 13 treatment period 4 vs Cohort 11 treatment period 4
- Cohort 13 treatment period 5 vs Cohort 11 treatment period 5
- Cohort 15 treatment period 4 vs Cohort 11 treatment period 4
- Cohort 15 treatment period 5 vs Cohort 11 treatment period 5
- Cohort 15 treatment period 4 vs Cohort 13 treatment period 4
- Cohort 15 treatment period 5 vs Cohort 13 treatment period 5

Graphic presentation in the form of box plots will be also added to the exploratory analysis.

Statistical Analysis Plan

9. ANALYSIS OF PHARMACODYNAMICS

9.1. MEASUREMENTS

Concentration of uric acid in serum will be used as measure of PD for both drugs. The concentration-time profile of uric acid is used to determine PD parameters as described in section 9.3. PD parameters will be derived based on actual measurements and %CFB (%CFB = value of change from baseline at each time point / value of measurement at baseline * 100%) for each cohort and treatment period and overall where applicable.

The Parts A/B (Treatment periods 1-3 and 4-5 for cohorts 1-8, 10-12 respectively) will be presented together, Part C (cohorts 13 and 15) will be presented separately unless necessary for comparative analysis.

9.2. COLLECTION SCHEDULE

Venous blood samples with corresponding time post-dose for uric acid are shown in table below:

Cohorts 1-2

Period	Day	Time from start of dose for saline, h	Time from start of dose for SEL-037, h
1-3	0	0	-1 (0)
		1.5	0.5
		2	1
		3	2
		6	5
		9	8
		24	23
		168	167
		336	335
	504	503	
	672	671	
4-5	0	0	0
			0.5
			1
			1.5
			2
			3
			6
1	24		
7	168		

Statistical Analysis Plan

Period	Day	Time from start of dose for saline, h	Time from start of dose for SEL-037, h
	14		336
	21		504
	28**		672
	30***		720

* - pre-dose for next Treatment period

** - PD point for Treatment periods 4 as pre-dose for Treatment period6

*** - last point for Treatment period 5 only

Cohorts 3-8, 10, 11, 12

Period	Day	Time from start of dose for saline, h	Time from start of dose for SEL-037, h
1-3	0	0	-1 (0)
		1	0
		1.5	0.5
		2	1
		3	2
		6	5
		9	8
		1	23
		7	167
		14	335
		21	503
		28*	671
		4-5	0
	0.5		
	1		
	1.5		
	2		
	3		
	6		
1	24		
7	168		
14	336		
21	504		
28**	672		
30***	720		

* - pre-dose for next Treatment period

** - PD point for Treatment periods 4 as pre-dose for Treatment period6

*** - last point for Treatment period 5 only

Statistical Analysis Plan

Cohorts 13, 15

Period	Day	Time from start of dose for saline, h	Time from start of dose for SEL-037, h
1-5	0	0	-1 (0)
		1	0
		1.5	0.5
		2	1
		3	2
		6	5
		9	8
		1	24
		7	168
	14	336	
	21	504	
	28*	672	
	30**	720	

* - pre-dose for next Treatment period

** - last point for Treatment period 5 only

9.3. PHARMACODYNAMICS PARAMETERS

The following PD parameters will be calculated based on actual measurements of PD uric acid for each Cohort and Treatment period and Overall where possible:

C_{min}	Minimal observed serum concentration
T_{min}	Time of minimal observed serum concentration
CFB_{min}	Minimum observed change from baseline in serum concentration
$AUE_{CFBlast}$	Absolute value for Area under the change from baseline in effect-time curve from time zero to the time of the last quantifiable concentration (effect - uric concentration)
$TA_{AUE_{CFBlast}}$	Time adjusted area under the absolute value for effect-time curve from time zero to the time of last quantifiable concentration (effect - uric concentration)
T_{onset}	Time of onset of effect - first time point of reduction uric acid concentration >10% of baseline
$T_{resolve}$	Time of resolution of effect - first time point of return of uric acid concentration to baseline defined as <10% difference from pre-dose baseline
$T_{duration}$	Time of duration of effect, calculated as $T_{resolve} - T_{onset}$

The following PD parameters will be calculated based on %CFB of PD uric acid for each Cohort and Treatment period and Overall where possible

Statistical Analysis Plan

$\%CFB_{\min}$	Minimum %CFB in serum concentration
$AUE_{\%CFB_{\text{last}}}$	Absolute value for Area under the %CFB in effect-time curve from time zero to the time of the last quantifiable concentration (effect - uric concentration)
$TA_AUE_{\%CFB_{\text{last}}}$	Time adjusted area under the %CFB for effect-time curve from time zero to the time of last quantifiable concentration (effect - uric concentration)
# and % of patients with $SUA < 6$ in TP3	The number and % of patients maintaining sUA concentrations below 6 mg/dL at the end of treatment period 3
# and % of patients with $SUA < 6$ in TP5	The number and % of patients maintaining sUA concentrations below 6 mg/dL at the end of treatment period 5

9.3.1. Handling of Dropouts, Missing Data or Data Below the Lower Limit of Quantification

Missing concentration data for all subjects who are administered scheduled study treatments will be considered as non-informative missing and will not be imputed. No concentration estimates will be provided for missing sample values.

For the derivation of PD parameters, serum concentration summary, individual serum concentration versus time curves and mean concentration versus time graphs the following rules will apply:

- Concentration values below the assay's lower limit of quantification (BLQ) for all time points will be treated as zero
- The sampling time of pre-dose samples relative to dosing will also be treated as zero
- If the actual time of sampling is missing, the planned time may be used
- In case of discrepancy between the nominal time and time stamp on the sample concentration data, which affects the temporal order of PD samples and is not related to documented protocol deviations, the nominal (planned) time will be used only for the pre-dose samples before treatment period 1. All other data with such time discrepancy will be removed from PD parameter derivations and summaries. The profiles for subjects with the single PD points removed due to this type of discrepancy can still be used for derivation of PD parameters and any summaries or models for other PD time points.

Statistical Analysis Plan

Samples taken outside the sampling windows may be excluded from by-time point summary statistics. This will be determined prior to the start of analyses around database lock.

No further imputation will be applied to any missing values.

